CLINICAL TRIAL PROTOCOL

Document Number:		c02441868-07
EudraCT No.:	2014-005395-28	
BI Trial No.:	1336.1	
BI Investigational Product(s):	BI 836880	
Title:	A First-in Human Phase I, non-randomized, open-label, multi-center dose escalation trial of BI 836880 administered by repeated intravenous infusions in patients with solid tumors.	
Brief Title:	Dose finding study of BI836880 in patients with solid tumors	
Clinical Phase:	Phase I	
Trial Clinical Monitor:	[REDACTED] Phone: [REDACTED] Fax: [REDACTED]	
Coordinating Investigator:	[REDACTED] Phone: [REDACTED] Fax: [REDACTED]	
Status:	Final Protocol (revised protocol based on global amendment 5)	
Version and Date:	Version:	Date:
	6.0	08 March 2019
Page 1 of 103		
Proprietary confidential information. © 2019 Boehringer Ingelheim International GmbH or one or more of its affiliated companies. All rights reserved. This document may not - in full or in part - be passed on, reproduced, published or otherwise used without prior written permission.		

CLINICAL TRIAL PROTOCOL SYNOPSIS

Name of company:	Boehringer Ingelheim		
Name of finished product:	not applicable		
Name of active ingredient:	BI 836880		
Protocol date: 11 May 2015	Trial number: 1336.1		Revision date: 08 March2019
Title of trial:	A First-in Human Phase I, non-randomized, open-label, multi-center dose escalation trial of BI 836880 administered by repeated intravenous infusions in patients with solid tumors.		
Coordinating Investigator			
Trial site(s):	Multi-centre trial conducted in 2 countries		
Clinical phase:	Phase I; First In Human		
Objective(s):	Objective of this trial is to determine the maximum tolerated dose (MTD) of BI 836880 and to provide preliminary safety data given as intravenous infusion and to determine recommended phase II dose. Further the PK-, immunogenicity and PD-profile, as well as primary signs of anti-tumor activity of BI 836880 should be assessed.		
Methodology:	Non-randomized, uncontrolled, open-label, dose escalating study of BI 836880 administered intravenously		
No. of patients:	About 80 patients will be entered, including at least 12 patients treated at MTD with tumour lesions evaluable for Dynamic contrast-enhanced (DCE)-MRI.		
total entered:	80		
each treatment:	80 (all patients will receive trial drug, but on different dose levels)		

Name of company:	Boehringer Ingelheim	
Name of finished product:	not applicable	
Name of active ingredient:	BI 836880	

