2.3 BENEFIT - RISK ASSESSMENT

BI 836880 has not been tested in human so far. In the 13 weeks toxicology study in cynomolgus monkeys BI 836880 was well tolerated up to the highest tested dose of 60 mg/kg.

Anti-VEGF or anti-VEGF-R antibodies have been largely tested in clinic with a well-defined safety profile. Most commonly reported adverse events with such compounds are fatigue, hypertension, proteinuria, diarrhea and bleeding (epistaxis). Severe adverse events include gastrointestinal perforations, tumor haemorrhage and arterial thromboembolism ([R14-3588](#), [R14-3261](#)).

There is less clinical experience with anti-Ang2 compared to VEGF pathway blockade clinical experience. The most advanced anti-angiopoietin compound (Trebaninib) in development is in Phase III in combination with chemotherapy [R14-5440](#). Other anti-Ang2 compounds are currently in early stage of clinical development ([R15-1645](#), [R15-1646](#), [R15-1648](#)). From this clinical experience the most commonly reported side effects are fatigue and gastro-intestinal symptoms (diarrhea, nausea and vomiting). No bleeding or thromboembolic events were reported with this class of compound. Of note, almost all tested anti-Ang2 molecules failed to define a MTD ([R15-1646](#), [R15-1648](#)).

Limited clinical experience of dual blockade is available. Recently, Phase I data of the bispecific human anti-Ang2/anti VEGF-A antibody (RG7221) were reported. MTD was not reached with only one dose limiting toxicity (DLT) reported (fatal pulmonary hemorrhage). Hypertension was the most common observed adverse event ([R15-1644](#)).

Based on this clinical available data it is expected that blockade of both targets will result in similar side effects as anti-VEGF and anti-Ang2 blockade. Based on the phase I trial results of RG7221 no increase in side effect severity is anticipated with BI 836880. It is anticipated that the safety profile of BI 836880 will most likely includes fatigue, hypertension, proteinuria, gastro-intestinal side effects and bleeding.

Previous clinical experience with nanobodies in different disease showed acceptable safety profile with no specific side effect related to this technology ([R13-2303](#)).

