If DLTs are observed in the first two consecutive patients of a previously untested dose level, subsequent enrolment to that cohort will be stopped. The Bayesian logistic regression model will be re-run to confirm that the dose-level still fulfils the EWOC criterion. Decision will be made whether the next patients will be enrolled on the same dose level, or if they will be enrolled to a lower dose level. [Figure 3.1: 1](#) shows how the decision of dose escalation is made.

[figure not shown]

Figure 3.1: 1: Escalation Decision – Combination of clinical and statistical expertise

BI 836880 infusion will be repeated every 3 weeks. In the case the patient shows a stable disease or even a response, the administration of BI 836880 can be continued up to disease progression or until intolerable toxicity has been recorded. In specific cases an intra-patient dose escalation can be granted (see [section 4.1.3](#)).

Once a MTD has been reached it is foreseen to enroll up to 12 patients on this dose level to enlarge the group of patients treated on proposed RP2D. A minimum of 12 patients must have tumour lesions evaluable for Dynamic contrast-enhanced (DCE)-MRI to allow a better interpretation of a pharmacodynamics (vascular) effect of BI 836880. Confirmation of the RP2D will be made based on all available safety, PK and Pharmacodynamics (PD) data at all treatment cycles and all dose levels.

In case of anti-tumor activity signals in a given tumor type, DSB can take the decision for a trial expansion to recruit patients with the same tumor type with the aim to generate safety and preliminary efficacy data specific to such disease. 2-3 tumor type expansion cohorts are planned. Up to a total of 20 patients may be recruited in each tumor type expansion cohort and will be treated according to same [Flow Chart](#) as patient in previous cohorts. This is to confirm RP2D in patient with specific tumor type according to study objective and to prepare further Phase II studies. This change will be implemented with a further amendment to this protocol.

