4.1.3 Selection of doses in the trial

Starting Dose

Maximum safe starting dose was estimated using different methods taking in account all available nonclinical information, including PK/PD and toxicity data. The starting doses from these calculations were compared. The lowest dose derived from these calculations is recommended for the maximum safe starting dose (see Investigator's Brochure for more details ([c02353882-01](#))).

The recommended starting dose is 0.67 mg/kg, correlates to a total dose of 40 mg.

Dose escalation Scheme

Furthermore, the PK/PD modelling provided information on the number of doses needed to reach a steady state the targeted concentration that allow a continuous high level target coverage ($\geq 90\%$). In an every 3 weeks schedule, C_{trough} plasma concentrations at steady state above the targeted C_{min} are expected be achieved after 3 infusions of BI 836880 at dose of 6 mg/kg (360 mg) and 1 infusion of BI 836880 at dose of 12 mg/kg (720 mg).

To minimize the number of patients to be treated at a non-therapeutic dose (below targeted concentration) within an acceptable time to steady state, a maximum of 200% dose increment will be applied for dose levels up to 120 mg. Dose escalation $\geq 120\text{mg}$ will not exceed 100% dose increment. No dose adaptation to body weight or body surface will be made. All patients

at the same dose level (DL) will be treated with the same total dose. [Table 4.1.3: 1](#) shows potential dose levels to be tested.

Table 4.1.3: 1 Potential dose levels

Dose level	Total dose (mg)	Maximum dose increment
DL 1	40	200%
DL 2	120	200%
DL3	360	100%
DL4	720	100%
DL5	1000	100%
DL6	1440 Limited to 1250*	

Intermediate dose levels can be tested based on DSB decision.

*Maximum dose that can be tested due to excipient limitation

Whenever a dose escalation step is to be performed (or: a new cohort will be opened for recruitment), the data of previous dose cohorts with priority on DLTs will be reviewed and discussed within the DSB. DSB can decide to increase the dose, expand the tested cohort or to test an intermediate dose level.

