A summary of the prior distribution is provided in [Table 7.1:1](#). Additionally, the prior probabilities of DLT at different doses, as well as the corresponding probability of under-, targeted and overdosing, are shown in [Table 7.1:2](#). Graphically, the prior medians with accompanying 95% credible intervals are shown in [Figure 7.1:1](#). As can be seen from both, the Table and the Figure, the prior medians of the DLT probabilities are in-line with the prior medians derived from the weakly informative prior, and the uncertainty around the medians is large, showing the low amount of information this prior provides. This is also supported by the prior sample size, i.e. the information contained in the prior. This is approximately equal to 1.2 patients, i.e. less than or around half of the weight the first cohort in the study will have.

Table 7.1: 1 Summary of prior distribution

Prior Component	Mixture Weight	Mean vector	SD vector	Correlation
1: Weakly inf.	0.900	-0.333 0.647	2.000, 1.000	0.000
2: High Tox	0.050	0.419 -0.274	2.000, 1.000	0.000
3: Low Tox	0.050	-3.316 0.042	5.000, 0.010	0.000

Table 7.1: 2 Prior probabilities of DLT at selected doses

Dose	Probability of true DLT rate in			Mean	SD	Quantiles		
	[0–0.16)	[0.16–0.33)	[0.33–1]			2.5%	50%	97.5%
40	0.877	0.049	0.074	0.069	0.172	<.001	0.001	0.703
120	0.813	0.071	0.116	0.104	0.208	<.001	0.006	0.812
360	0.685	0.110	0.205	0.176	0.258	<.001	0.043	0.899
720	0.515	0.153	0.332	0.274	0.295	<.001	0.148	0.944
1250	0.269	0.164	0.566	0.444	0.318	0.005	0.410	0.975

Doses printed in bold face meet the overdose criterion ($P(\text{overdose}) < 0.25$)

[figure not shown]

Figure 7.1: 1 Prior medians and 95% credible intervals

The MTD may be considered reached if the following criteria is fulfilled

1. At least 1 DLT on the trial and either
2. At least 6 patients haven been treated at the MTD and the posterior probability of the true DLT rate in the target interval (16%-33%) is above 50%, OR
3. At least 18 patients in the trial with 6 patients have been treated at MTD.

Statistical model assessment

The model was assessed using two different metrics:

1. Hypothetical data scenarios: for various potential data constellations as they could occur in the actual trial, the maximal next doses as allowed by the model and by the 100% escalation limit are investigated. Data scenarios thus provide a way to assess the “on-study” behaviour of the model.

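### If 1250 mg is well tolerated, protocol 7.1 and the SAP give conflicting MTD conclusions, and a single DLT decides which label the protocol permits

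*Protocol*

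**What the plan says.** **MTD rule, protocol 7.1.** The section opens with the idea that the MTD is reached when the probability of the 16%-33% target interval is large enough. The operational list then requires "At least 1 DLT on the trial and either" of two routes:
- Criterion 2: at least 6 patients at the dose and "posterior probability of the true DLT rate in the target interval (16%-33%) is above 50%, OR"
- Criterion 3: "At least 18 patients in the trial with 6 patients have been treated at MTD", with no condition on the posterior.

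**MTD definition, SAP.** SAP 5.1 and 7.4 define the MTD as the highest dose whose risk of a DLT rate above 33% is below 25%. No DLT is required. SAP 5.1 adds the general target-interval clause for when the MTD is reached; SAP 7.4 does not.

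**Dose ceiling, protocol 4.1.3.** The last level is limited to 1250 mg: "Maximum dose that can be tested due to excipient limitation".

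**Background, protocol 2.3.** It notes that "almost all tested anti-Ang2 molecules failed to define a MTD", and for the dual Ang2/VEGF-A antibody that "MTD was not reached with only one dose limiting toxicity (DLT) reported".

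**Cohort linked to the MTD.** Section 3.1 says "Once a MTD has been reached it is foreseen to enroll up to 12 patients" at that dose, and the synopsis plans about 80 patients, "including at least 12 patients treated at MTD with tumour lesions evaluable for Dynamic contrast-enhanced (DCE)-MRI". Inclusion criterion 2 also refers to the MTD. Section 5.3.2 instead places up to 12 patients on the proposed RP2D.

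**The concern.** The top dose is fixed by formulation, not toxicity, so dose finding may end with the drug still well tolerated. No passage states what is then concluded about the MTD. The result depends on which document is read and on whether one DLT happened to occur. With none, protocol 7.1 cannot call the MTD reached, yet the SAP definition names 1250 mg. With one, criterion 3 allows the label although the model says the dose is probably below target, which contradicts 7.1's own statement of what reaching the MTD means. The MTD assessment is the primary endpoint, so the stated rules could report the same drug either way.

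**Working it through.** **1. Reproduce the plan's figures.** The model is logit p(d) = log α + β·log(d/d*), with the three-component prior of Table 7.1:1, integrated on a grid.

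| Quantity | Protocol | d* = 1250 mg | d* = 720 mg (as printed) |
|---|---|---|---|
| Prior P(over) at 720 mg | 0.332 | 0.335 | 0.570 |
| Table 10.6:1 scenario 6, P(over) at 720 mg | 0.025 | 0.024 | 0.076 |
| Table 10.6:1 scenario 7, P(over) at 720 mg | 0.224 | 0.225 | 0.389 |

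The tables reproduce only with d* = 1250 mg, so that value is used below. The printed reference dose and the tables need reconciling, but that is a separate matter.

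**2. One trial path, two endings.** Take no DLT in 2 patients at 40 mg, 2 at 120, 3 at 360, 3 at 720 and 3 at 1000 mg, then 6 patients at 1250 mg: N = 2+2+3+3+3+6 = 19. The step to 1250 mg is allowed, because P(over) there after 0/3 at 1000 mg is 0.169, below 0.25.

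| At 1250 mg | P(under) | P(target) | P(over) | Protocol 7.1 | SAP overdose definition |
|---|---|---|---|---|---|
| 0/6 | 0.898 | 0.092 | 0.010 | No MTD (criterion 1 fails) | 1250 mg |
| 1/6 | 0.586 | 0.328 | 0.086 | MTD permitted (criterion 3) | 1250 mg |

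A finer grid changes these by no more than 0.01 (0.596 / 0.321 / 0.083 for 1/6). Using d* = 720 mg gives nearly the same answers (0.909 / 0.082 / 0.008 and 0.597 / 0.325 / 0.079), so this step does not depend on the reference-dose question. With 0/6, the target-interval clause in SAP 5.1 is also unmet, so SAP 5.1 names a dose that its own clause would not call reached. A single DLT at 360 mg with 0/6 at 1250 mg also satisfies criterion 3 (0.731 / 0.243 / 0.027).

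**3. How often.** The true DLT rate is not in the documents, so a range is assumed. For scale, at a constant rate p, P(no DLT in n patients) = (1-p)^n. For n = 18 this is 0.98^18 = 69.5%, 0.95^18 = 39.7% and 0.90^18 = 15.0%. For n = 40 it is 44.6%, 12.9% and 1.5%.

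The protocol's rules were then simulated: 1000 trials per row, the five doses of Table 10.6:2, cohorts of 3, the 0.25 overdose limit, the escalation limits and the three criteria. The true rate rises to the stated value at 1250 mg, and enrolment stops at the first cohort reaching 40. A trial counts as declaring an MTD as soon as the criteria permit it.

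| True rate at 1250 mg | No MTD because of zero DLTs | MTD declared (true rate always under target) | Declared on exactly one DLT (% of all trials) |
|---|---|---|---|
| 1% | 72.7% | 27.1% | 26.5% |
| 2% | 49.9% | 50.0% | 47.5% |
| 3% | 33.5% | 66.3% | 61.9% |
| 5% | 17.6% | 81.9% | 71.5% |
| 8% | 6.4% | 92.6% | 73.2% |
| 10% | 4.0% | 94.5% | 67.0% |

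Almost all declarations came through criterion 3 with P(target) not above 50% (81.5 of the 81.9 points at 5%). Adding the 1000 mg level gives 71.1% to 3.7% in the second column. As a check, the same code on the protocol's low-toxicity truth gives 25.1% under and 74.6% target with mean N 19.35, against 26.2%, 73.8% and 19.77 in Table 10.6:3. Other scenarios match only roughly (scenario 1 target 52.5-58.5% against 61.6%), because the protocol does not give its simulation's cohort-size rule.

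**4. What the plan simulated.** True rates at 1250 mg in Table 10.6:2 are 0.444, 0.603, 0.250, 0.380 and 0.600. None is below 16%, and every row of Table 10.6:3 has a minimum of 1 DLT.

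**The case against.** Several points on the other side stand.

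- **Discretion.** Section 7.1 says the MTD may be considered reached, and under 5.3.2 the DSB may recommend stopping and weighs all safety and PK/PD data. A reader might infer that one DLT automatically produces an MTD. It does not: the DLT is necessary, not sufficient, and the label is permitted rather than forced.
- **RP2D.** A reader might infer that the primary objective goes unanswered. That objective also covers the RP2D, and 7.3.1 allows a different dose to be recommended. The 5.3.2 route (sufficient efficacy while a higher dose is still recommended) does not literally apply at 1250 mg, but 7.3.1 has no such limit.
- **Confirmation group.** A reader might infer that the 12-patient group has no trigger. Section 5.3.2 already ties it to the proposed RP2D; only the DCE-MRI wording rests on the MTD.
- **Likelihood.** A reader might infer that the sponsor expects no MTD. The broad statement in 2.3 concerns anti-Ang2 agents. The dual antibody had one DLT, which would have met criterion 1, and the main prior component puts a median 20% DLT rate at 720 mg.
- **Zero-DLT data.** Scenario 6 of Table 10.6:1 does examine a path with no DLT up to 720 mg, so the case was not ignored. It gives no end rule, however.
- **Rationale.** Requiring an observed DLT before naming an MTD is a defensible choice. Simply deleting criterion 1 would be worse, since 0/6 at 1250 mg would then qualify under criterion 3.

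None of this removes the conflict between the protocol criteria and the SAP definition, or the lack of a posterior condition in criterion 3.

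**Conclusion.** The point holds as a conflict over the MTD conclusion when the highest testable dose is well tolerated. The 0/6 and 1/6 comparison follows from the printed rules and prior and needs no assumed true rate. The frequencies do rest on assumptions: the true rate and its shape over dose, cohorts of 3, about 40 patients, and a DSB that applies the criteria as soon as they permit. Zero DLTs then block an MTD in about 50% of trials at a top-dose rate of 2%, 18% at 5% and 4% at 10%. The blocking problem is therefore material only for a drug of very low toxicity. Labelling an under-target dose as MTD persists across the whole range, in 27% to 95% of trials. The documents do not support the wider reading that the trial cannot answer its primary objective.

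**What to change.** 1. Reconcile the MTD definitions in protocol 7.1 and SAP 5.1 and 7.4. Add a third outcome, *MTD not reached in the tested range*. It applies, with or without a DLT, when the highest testable dose has at least 6 evaluable patients, meets the overdose criterion and is more probably under target than in target. Criterion 3 should not be able to label such a dose an MTD. The sponsor should set the exact cut-off by simulation, because a strict one will misclassify: at a true rate of 25%, one DLT or fewer in six patients has probability 0.75^6 + 6·0.25·0.75^5 = 0.178 + 0.356 = 53%.
2. Reconcile the DCE-MRI wording in the synopsis, 3.1 and inclusion criterion 2, which refers to the MTD, with 5.3.2, which refers to the proposed RP2D.
3. Add a simulation scenario to Appendix 10.6 with every dose below 16%, reporting how often each of the outcomes occurs.

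The cost is amendment wording and one further simulation. The downside is that the trial may formally report no MTD. Protocol 6.2.2 mentions only 2 ongoing patients, which suggests that recruitment has ended. If so, the change affects reporting rather than enrolment, and an outcome defined after the DLT data are known should be described as such in the report.

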3. DESCRIPTION OF DESIGN AND TRIAL POPULATION

3.1 OVERALL TRIAL DESIGN AND PLAN

This is a Phase I, non-randomized, uncontrolled, open-label, dose escalating study of BI 836880 administered intravenously. The eligible patient population will be patients with advanced solid tumors. Dose escalation will be guided by a Bayesian logistic regression model with over dose control (details refer to [Section 7](#)), restricted to a maximum of 200% dose increment for dose up to 120 mg and a maximum of 100% dose increment for dose >120 mg. At any time during the trial, it will not be permitted to escalate to a dose which does not fulfil the escalation with overdose control (EWOC) criterion (refer to Section 7).

For any dose-escalation cohort, at least 2 patients will be required. At first dose level, first patient will be treated and observed for at least 2 weeks before allowing the second patient to receive BI 836880 infusion. Subsequent enrollment at all dose levels within dose escalation, each patient in a given cohort (dose level) will be observed for a minimum of 48 hours after first BI 836880 application before allowing treatment for subsequent patient in the same cohort. In case only 2 patients are evaluable and neither has experienced a DLT within the first cycle, then dose-escalation can occur based on these 2 patients. However, should one of these 2 patients experience a DLT in the first cycle, a third patient will be enrolled on the same dose level. After all patients in a cohort have either experienced a DLT or have been observed for at least one cycle (=3 weeks) without a DLT, the Bayesian model will be updated with the newly accumulated data. The overdose risk will then be calculated for each dose, and escalation will be permitted to all doses which fulfil the EWOC criterion and dose escalation rules according to [section 4.1.3](#). Decision on further recruitment (dose escalation, de-escalation or cohort expansion will be made by a Data Safety Board (DSB) based on the collected safety data as well as other data (e.g. PK/PD data) when available.

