7. STATISTICAL METHODS AND DETERMINATION OF SAMPLE SIZE

7.1 STATISTICAL DESIGN – MODEL

This is phase I, open-label, dose-escalating trial to determine the MTD and RP2D for BI 836880 in patients with solid tumor. The MTD may be considered reached if the probability that the true DLT rate is in target interval (16% - 33%) is sufficiently large. Dose escalation and determination of MTD will be guided by a Bayesian 2-parameter logistic regression model with overdose control ([R13-4803](#); [R13-4806](#)). These designs have been shown to be superior regarding the precision of MTD determination compared to 3+3 designs and have been particularly endorsed by the FDA ([R13-4881](#)).

The model is formulated as follows:

$$\text{logit}(p(d)) = \log(\alpha) + \beta * \log(d/d^*),$$

where $\text{logit}(p) = \log(p/(1-p))$.

$p(d)$ represents the probability of having a DLT in the first cycle at dose d , $d^* = 720\text{mg}$ is the reference dose, allowing for the interpretation of α as the odds of a DLT at dose d^* , and $\theta = (\log(\alpha), \log(\beta))$ with $\alpha, \beta > 0$ is the parameter vector of the model.

Since a Bayesian approach is applied, a prior distribution $\pi(\theta)$ for the unknown parameter vector θ needs to be specified. This prior distribution will be specified as a mixture of three multivariate normal distributions, i.e.

$$\pi(\theta) = \varphi_1 \pi_1(\theta) + \varphi_2 \pi_2(\theta) + \varphi_3 \pi_3(\theta)$$

with

$\varphi_i, i = 1, 2, 3$ the prior mixture weights ($\varphi_1 + \varphi_2 + \varphi_3 = 1$)

and

$$\pi_i(\theta) = \text{MVN}(\mu_i, \Sigma_i)$$

the multivariate normal distribution of the i -th component with mean vector μ_i and covariance matrix Σ_i , with

$$\Sigma_i = \begin{pmatrix} \sigma_{i,11}^2 & \sigma_{i,11}\sigma_{i,22}\rho_i \\ \sigma_{i,11}\sigma_{i,22}\rho_i & \sigma_{i,22}^2 \end{pmatrix}$$

Mixture prior distributions have the advantage that they allow for specification of different logistic dose-toxicity curves, therefore making the prior more robust.

Prior derivation

For the current study, no relevant information in the form of human data was available, since no study in a comparable population has been conducted. Therefore, the three mixture components were established as follows:

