4. CHANGES IN THE PLANNED ANALYSIS OF THE STUDY

5. ENDPOINT(S)

5.1 PRIMARY ENDPOINT(S)

The objective of this study is to determine the safety and tolerability of BI 836880. The primary endpoint is the determination of the maximum tolerated dose (MTD) of BI 836880 based on the number of patients with dose-limiting toxicities (DLTs) during the first treatment cycle. The DLT is defined in section 5.3.1 of the CTP.

The MTD is defined as the highest dose with less than 25% risk of the true DLT probability being above 33%, and may be considered reached if the probability that the true DLT rate is in target interval (16%-33%) is sufficiently large during the MTD evaluation period.

The DLT evaluation period is defined as the time within 3 weeks after first administration of study treatment. The evaluation period will be extended to two more weeks if treatment is delayed due to a drug related AE, For further details, please see CTP section 5.3.1.

Patients, who have not completed first cycle of treatment for other reason than DLT, will be replaced. Patients who were replaced during the MTD evaluation period will not be considered for MTD determination. Those patients that have completed the MTD evaluation period without having been replaced will be referred to as patients evaluable for MTD.

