7.4 PRIMARY ENDPOINT(S)

The primary endpoint is to assess the MTD based on the number of patients presenting DLTs during the MTD evaluation period. The primary analysis is for the determination of the MTD. The purpose of this analysis is to summarize and document the data that led to the selection of the MTD. Therefore, an overall summary of DLTs (see CTP section 5.3.1 for the definition of DLTs) which occurred during the MTD evaluation period will be provided for each dose cohort from the dose finding cohort treated set. Patients, if any, who did not complete the MTD evaluation period for reasons other than DLT will be excluded from the analysis of the primary endpoint.

A summary of the number of patients with DLTs overall in any course will be also given by initial treatment and displayed in a similar format to the summary of DLTs occurring in the MTD evaluation period.

The analysis of the MTD is based on a Bayesian logistic regression model (BLRM) guided by the escalation with overdose control principle. The MTD is defined as the highest dose for a given schedule that is expected to cause less than 25% risk of the true DLT rate being above or equal to 33% during the MTD evaluation period. Estimation of the MTD during the dose escalation phase of the study will be based upon the estimation of the posterior probability of the incidence of DLT in toxicity categories during the MTD evaluation period for all evaluable patients. The model to be used is specified in CTP section 7.

The posterior probabilities that the toxicity rates of each dose level fall into the categories specified in CTP section 7 will be displayed.

[figure not shown]

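### The MTD criteria listed in protocol 7.1 carry no overdose limit, so at high observed toxicity they permit declaring a dose that the SAP's definition of the MTD excludes

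*Protocol*

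**What the plan says.** Protocol 5.3.2 refers to section 7 for the detailed definition of the MTD. The list in protocol 7.1 has three parts:

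- Criterion 1: "At least 1 DLT on the trial and either" one of the next two.
- Criterion 2: "At least 6 patients haven been treated at the MTD and the posterior probability of the true DLT rate in the target interval (16%-33", where that probability must exceed 50%.
- Criterion 3: "At least 18 patients in the trial with 6 patients have been treated at MTD".

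The overdose limit appears elsewhere in the protocol. A footnote to Table 7.1:2 says "Doses printed in bold face meet the overdose criterion" and gives that criterion as P(overdose) < 0.25, where overdose means a true DLT rate of 33% or more. Section 3.1 applies it to escalation: "it will not be permitted to escalate to a dose which does not fulfil the escalation with overdose control (EWOC) criterion". The same section re-checks a dose if the first two consecutive patients at an untested level both have DLTs. The opening of 7.1 adds a general statement: "Dose escalation and determination of MTD will be guided by a Bayesian 2-parameter logistic regression model with overdose control".

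The SAP puts the limit into the definition. Section 5.1: "The MTD is defined as the highest dose with less than 25% risk of the true DLT probability being above 33"%, followed in the same sentence by the condition that the target-interval probability be sufficiently large. Section 7.4: "The MTD is defined as the highest dose for a given schedule that is expected to cause less than 25% risk" of a true DLT rate at or above 33%.

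**The concern.** The MTD is the primary endpoint. The group of up to 12 patients at that dose and the proposed RP2D follow from it. The protocol gives an explicit list of conditions for declaring it, and none of them bounds the probability that the dose is too toxic. The EWOC sentence in 3.1 governs moving up to a dose. It does not govern naming the current dose as the MTD after further DLTs have been seen there. The SAP definition does bound that probability. If the two rules separate on data the trial could produce, the DSB would have two written rules for the primary endpoint, and neither document says which prevails.

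**Working it through.** **Inputs** (protocol 7.1). Model: logit p(d) = log α + β·log(d/d*). Mixture prior on (log α, log β): weights 0.9, 0.05, 0.05; means (−0.333, 0.647), (0.419, −0.274), (−3.316, 0.042); SDs (2, 1), (2, 1), (5, 0.01); correlations 0. Posterior ∝ prior × ∏ p(d)^x·(1−p(d))^(n−x), integrated on a grid. P(target) = Pr(0.16 ≤ p < 0.33); P(OD) = Pr(p ≥ 0.33).

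**Step 1: reproduce the plan's own figures.** The protocol states d* = 720 mg, but the printed prior means correspond to 1250 mg. For component 1, with median DLT rates of 0.1% at 40 mg and 20% at 720 mg:

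- slope β = (−1.386 + 6.907)/ln(18) = 5.521/2.890 = 1.910, and ln β = 0.647, as printed;
- log-odds at 720 mg = −1.386;
- log-odds at 1250 mg = −1.386 + 1.910 × ln(1250/720) = −1.386 + 1.054 ≈ −0.333, which is the printed mean.

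With d* = 1250 the largest difference from Table 7.1:2 is 0.004 and from Table 10.6:1 is 0.014; scenario 7 gives P(OD) 0.224 at 720 mg against a printed 0.224. With d* = 720 the differences reach 0.25 and 0.17. I use 1250 for the main results and 720 as a sensitivity check.

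**Step 2: what the criteria imply.** The three interval probabilities sum to 1, so P(target) > 0.50 forces P(OD) < 0.50. That is the only bound in criterion 2. Criterion 3 contains no posterior probability and so gives no bound.

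**Step 3: apply both rules to the same data.** After 0/2 at 40 mg, 0/2 at 120 mg and 0/3 at 360 mg, with 12 patients at 720 mg (N = 2+2+3+12 = 19):

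| DLTs at 720 mg | P(target) | P(OD), d* = 1250 | 7.1 criteria met at 720 mg | P(OD) < 0.25 |
|---|---|---|---|---|
| 3/12 | 0.53 | 0.15 | 2 and 3 | yes |
| 4/12 | 0.54 | 0.33 | 2 and 3 | no |
| 5/12 | 0.40 | 0.56 | 3 only | no |

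For 4/12 the highest tabulated dose with P(OD) < 0.25 is 360 mg (P(OD) 0.015).

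A second path isolates criterion 3: 0/3, 0/3 and 0/6 at 40, 120 and 360 mg, then 3/6 at 720 mg (N = 18). It gives P(OD) about 0.50 at 720 mg, with P(target) below one half.

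**Step 4: could the trial get there under EWOC?** Take the 4/12 as cohorts of 0/3, 1/3, 1/3 and 2/3. P(OD) at 720 mg before each cohort is 0.114, 0.024, 0.075 and 0.117, so each could be enrolled. Only the last result lifts it to 0.333. The 5/12 case follows the same path with 3/3 in the last cohort. At the scenario 1 rate for 720 mg in Table 10.6:2 (0.274), P(at least 4 DLTs in 12) = 1 − Σ(k=0..3) C(12,k)·0.274^k·0.726^(12−k) = 0.43. This figure is not conditional on the escalation path.

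**Step 5: sensitivity to d*.** With d* = 720, P(OD) is about 0.44 for 4/12 (P(target) about 0.48, so criterion 3 only) and 0.66 for 5/12. The end-of-data conflict remains. However, P(OD) before the first 720 mg cohort would then be about 0.34, so EWOC would have blocked this particular path.

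**The case against.** The strongest reply is that the protocol and SAP together form one rule. The opening of 7.1 ties MTD determination, as well as escalation, to a model with overdose control. Criteria 2 and 3 count patients at the MTD, so they can be read as saying when an already identified dose is established, while the SAP says which dose it is. SAP 5.1 joins the two elements in one sentence.

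The appendix points the same way: scenario 5 of Table 10.6:1 de-escalates at P(OD) 0.575, and scenario 2 offers no dose at 0.278. In a simulation under assumed cohort rules, over-dose declarations in row 4 of Table 10.6:2 were 9.0% under the literal criteria and 5.1% to 5.6% with the limit added; Table 10.6:3 prints 5.7%. This is suggestive only, because the protocol does not print its simulation rules.

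Most of this stands as evidence of intent. It does not close the gap. Being guided by a model is not a condition that can be checked, the explicit list omits the limit, and criterion 3 uses no model output.

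A reader might infer three stronger things that the documents do not support:

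- **That the trial lacks overdose control.** EWOC governs escalation, and 7.1 links it in general terms to MTD determination.
- **That the two documents generally give different MTDs.** They agree on many data sets, as 3/12 shows.
- **That the protocol would force declaration of an excessive dose.** The wording is permissive, and the DSB decides on all available data.

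**Conclusion.** The point holds as a gap in the listed criteria and an unreconciled difference between protocol 7.1 and SAP 5.1 and 7.4. Criterion 3 is the larger gap, because it sets no cap; criterion 2 allows P(OD) up to 50%, twice the SAP's 25%. The conflict appears when observed toxicity is high: at 4/12 and 5/12 at 720 mg, P(OD) is about 0.33 and 0.56, and 7.1 permits a declaration that the SAP definition excludes.

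These sizes rest on the printed prior with d* = 1250, the value that reproduces the protocol's tables. With the stated d* = 720 the conflict on those data remains, subject to the path caveat above.

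How often it would occur is uncertain. Simulations of the literal criteria put an MTD at a dose with P(OD) ≥ 0.25 in roughly 10% to 18% of trials. Estimates of the rise in truly over-dosing declarations in the high-toxicity scenario differ with implementation (12.8% to 19.6% in one, 13.3% to 17.6% in another). Treat these as indicative only. The posterior examples carry the argument.

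**What to change.** Reconcile the passages so that one rule applies. In protocol 7.1, state that any dose declared MTD under criterion 2 or 3 must also meet the documents' own overdose criterion, P(DLT rate ≥ 33%) < 0.25, on the data used for the declaration. Carry the same rule into protocol 5.3.2 and SAP 5.1 and 7.4. Use one boundary in both SAP sections, since 5.1 says above 33% and 7.4 says at or above; under this continuous posterior the choice does not change the probability.

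The cost is one sentence in 7.1 and matching text elsewhere, with no added patients. The downside is more declarations at under-dosing levels in some scenarios than under the literal criteria. Estimates run from about 3 to about 10 percentage points, depending on simulation rules that the protocol does not print. The SAP definition already implies that cost.
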